#### **4.5 EFFICACY ANALYSIS**

Clinical endpoints, biomarkers and pharmacodynamic parameters considered for analysis are outlined in the sub-sections below. The population to be used for the analysis is the ITT evaluable population unless stated otherwise.

Given the exploratory nature of HD app digital endpoints, analyses similar to the one described below will be performed for digital endpoints as listed in Section [2.2.3](#) (additional digital endpoints may be considered), with the objective of assessing the longitudinal changes over time and the relationship with clinical endpoint and biomarkers. Details of those analyses will be described in a separate SAP.

##### **4.5.1 Longitudinal Changes over Time**

The objective of this section is to describe the longitudinal changes over time, to understand disease progression, for all different clinical, digital and PD endpoints, while adjusting for known prognostic factors (such as CAG repeats). Data outside a time window of +- 56 days from the expected scheduled visit will not be used for analysis of summary tables and mean plots by visit.

For the primary and secondary endpoints descriptive tables will be used to summarize the different variables on absolute value, change from baseline and percentage change (where appropriate) from baseline by visit.

For continuous variables, spaghetti plots showing patient profiles and boxplots across time will be presented.

Where the numeric variable indicates an ordinal, rather than continuous, outcome, the analysis will focus on frequency counts and percentages by visit; no other summary statistics will be provided.

In order to model the change from baseline on each individual continuous parameter across time, a mixed-model repeated measures (MMRM) analysis will be applied. This model will include as covariates the baseline parameter, number of CAG repeats, baseline age, CAP, country (as categorical, only for outcome assessments [patient-, observer- and clinician-reported, and performance]) and time (as categorical). Data outside a time window of +- 56 days from the expected scheduled visit will not be used for this analysis. Estimates for the change from baseline based on the MMRM model, at each time-point and computed for the baseline average value of the other baseline covariate, along with corresponding standard error, 95% CI and unadjusted p-value will be presented. Technical details of the MMRM model (e.g. methods for the denominator degree of freedom, variance-covariance matrix, etc.) are given in [Appendix 3](#).

Although confidence intervals and p-values will be reported, no formal hypothesis testing will be considered.

A detailed list of outputs produced for each parameter for describing the longitudinal change over time is described in [Table 2](#).

The procedure that will be used to fit mixed-models in SAS is as follows (with Day 421 as example):

```
proc mixed data=dataname plots=all;
class subjid time Country;
model y-variable=Baseline_y-variable + CAG + CAP + Baseline_Age + Country + time;
repeated time / subject= subjid type=UN;
Estimate "Day 421"
  Intercept 1
  Baseline_y-variable &BASEY
  CAG &CAGBL
  CAP &CAPBL
  Baseline_Age &AAGE
  time 0 0~1
/ e cl alpha=0.05
run;
```

where &BASEY, &CAGBL &CAPBL and &AAGE will be fixed at the population average at baseline. Time contrast coefficients will be verified with the actual data and

thus the final version of the SAS code may differ from the example above depending on the ordering of the different levels.

Notice that the country variable will only be included when modelling outcome assessments [patient-, observer- and clinician-reported, and performance], pooling country across region (North America -USA plus Canada- vs EU) may be considered in case of convergence problems.

In case a significant number of visits will be delayed beyond the +-56 days, the following additional sensitivity analysis will be conducted, using all data available (irrespective of visit delay).

In order to model the change from baseline on each individual continuous parameter across time, a linear mixed effect model analysis will be applied. The model will include a random intercept and a random slope for the time of assessment (as continuous) . Additionally it will include as fixed effect the time of assessment (as continuous) , the baseline parameter, number of CAG repeats, baseline age, CAP, country (as categorical, only for outcome assessments [patient-, observer- and clinician-reported, and performance]). An unstructured variance covariance matrix will be used for the two random effects (in case of convergence issues, the two random effects will be assumed to be independent).

Least squares means (LSM) estimates for the change from baseline based on the model, at the time of interest, along with corresponding standard error, 95% CI and unadjusted p-value will be presented. The estimate for the fixed effect of time of assessment (population level slope) will be reported along with corresponding 95% CI. For each parameter, all available time-points will be used.

No formal hypothesis testing will be considered and results are presented descriptively with confidence intervals

A detailed list of outputs produced for each parameter for describing the longitudinal change over time is described in [Table 2](#).

The procedure that will be used to fit mixed-models in SAS is as follows with day 421 as example:

```
proc sort data=dataname;
by subjid time;
run;

proc mixed data=dataname plots=all;
class subjid Country;
model y-variable= Baseline_y-variable + Baseline_CAG + Baseline_CAP +
Baseline_Age + Country + time/Solution ;
random Intercept time/ sub= subjid type=un s;
Estimate "Day 421"
        Intercept 1
```

```

Baseline_y-variable &BASEY
CAG &CAGBL
CAP &CAPBL
Baseline_Age &AAGE
time 421
/ e cl alpha=0.05
run;

```

where &BASEY, &CAGBL &CAPBL and &AAGE will be fixed at the population average at baseline.

Notice that the country variable will only be included when modelling outcome assessments [patient-, observer- and clinician-reported, and performance]; pooling country across region (North America -USA plus Canada- vs EU) may be considered in case of convergence problems.

Linearity over time will be assessed and the linear mixed effect model will only be applied to endpoint with a monotonic pattern of change over time.

#### **4.5.1.1      Mutant Huntingtin protein in CSF**

For CSF mHTT, all statistical modeling will be based on the natural log-transformed parameter. Results on the modelling for the change from baseline will be back-transformed to derive the corresponding percent change in the geometric mean as explained in [Appendix 3](#).

Values below the lower limit of quantitation (BLQ) will be imputed as [The BLQ value]\*0.5. In case a sample has been assessed on more than one date then the value corresponding to the last measurement date will be used.

Descriptive tables and plots as well results from the MMRM model will be provided as described in Section [4.5.1](#) and [Table 2](#).

#### **4.5.1.2      CSF/Plasma Biomarkers**

Assessments of CSF biomarkers will include the following parameters:

- NfL
- Tau
- YKL-40

Additional parameters may be explored.

NFL is the only of the above biomarkers which is also assessed in plasma.

For CSF/plasma biomarkers (e.g. NfL), all statistical modeling will be based on the natural log-transformed parameter. Results on the modelling for the change from

baseline will be back-transformed to derive the corresponding percent change in the geometric mean as explained in [Appendix 3](#).

Values below the lower limit of quantitation (BLQ) will be imputed as [The BLQ value]\*0.5. In case a sample has been assessed with more than once then the value with the last measurement date will be used.

Descriptive tables and plots as well results from the MMRM model will be provided as described in Section [4.5.1](#) and [Table 2](#).

#### **4.5.1.3 Huntington's Disease Rating Scale**

The Composite Unified Huntington's Disease Rating Scale (cUHDRS) ([Schobel et al. 2017](#)) is defined as a combination of the following first 4 individual assessments:

##### **4.5.1.3.1 Total Functional Capacity**

The Total Functional Capacity (TFC) represents the Investigator's assessment of the patient's capacity to perform a wide range of activities of daily living including working, chores, managing finances, eating, dressing and bathing. It is based on a brief interview with the patient and, potentially, the trial partner. Individual item scores range from 0 to 3 (by 1), total score ranges from 0 to 13 and higher scores represent better functioning. The total score is the sum of the individual item scores.

The scale is considered completed if there are no missing values. There will be no imputation for missing values. The total score will be derived only if each of the individual item scores is not missing.

The individual items contributing to the total score are listed below:

- Occupation (0 to 3)
- Finances (0 to 3)
- Domestic chores (0 to 2)
- ADL (0 to 3)
- Care level (0 to 2)

##### **4.5.1.3.2 Total Motor Scale**

The Total Motor Scale (TMS) is the sum of the individual motor ratings obtained during administration of the motor assessment portion of the UHDRS. Individual item scores range from 0 to 4 (by 1), total score ranges from 0 to 124 and higher scores represent more severe impairment. Individual items contributing to the total score are listed below:

- Ocular Pursuit (two items: horizontal and vertical)
- Saccade Initiation (two items: horizontal and vertical)
- Saccade Velocity (two items: horizontal and vertical)

- Dysarthria
- Tongue Protrusion
- Finger Taps (two items: left and right)
- Pronate/Supinate-Hands (two items: left and right)
- Luria – Fist-Hand-Palm Sequencing
- Rigidity – Arms (two items: left and right)
- Bradykinesia - Body
- Maximal Dystonia (five items: trunk, RUE, LUE, RLE, LLE)\*
- Maximal Chorea (seven items: face, bol, trunk, RUE, LUE, RLE, LLE)\*
- Gait
- Tandem Walking
- Retropulsion Pull Test

(\*: RUE= right upper limb, LUE= left upper limb, RLE= right lower limb, LLE= left lower limb)

The scale is considered completed if there are no missing values.

For each of the scores (total or domains) if any of items is missing then there will be no imputation for missing data and the score will not be computed.

In addition to TMS total score, the 'maximal chorea in upper limb' item (left and right; from TMS) and the 'maximal chorea score' will also be considered. The maximal chorea score is the sum of the seven maximal chorea items (from TMS).

#### **4.5.1.3.3 Symbol Digit Modalities Test**

The Symbol Digit Modalities Test (SDMT) is used to assess attention, visuoperceptual processing, working memory and psychomotor speed. The patient must pair abstract symbols with specific numbers according to a translation key. The test measures the number of items correctly paired (maximum of 110) in 90 seconds.

The scale is not considered completed if there is no result available. There will be no imputation for missing data even if the patient is not able or refuses to complete the task.

#### **4.5.1.3.4 Stroop Word Reading Test**

The Stroop Word Reading Test (SWRT) is a measure of processing and psychomotor speed. Patients are presented with a page of color names printed in black ink and are asked to read aloud as many words as possible within a given amount of time (45 seconds in Study BN40422). The number of words read correctly is counted and higher scores indicate better cognitive performance. The raw score will be used for the analysis.

The scale is not considered completed if there is no result available. There will be no imputation for missing data even if the patient is not able or refuses to complete the task.

#### **4.5.1.3.5 cUHDRS**

Based on the aforementioned assessments, the following formula is used to derive the cUHDRS where TFC, TMS, SDMT and SWRT are the raw total scores of each assessment:

$$\text{cUHDRS} = \left( \frac{\text{TFC} - 8.8}{2.8} \right) - \left( \frac{\text{TMS} - 34.4}{17.4} \right) + \left( \frac{\text{SDMT} - 25.2}{12.4} \right) + \left( \frac{\text{SWRT} - 58}{21.2} \right) + 10.0$$

The cUHDRS will be derived only if each of the individual components is not missing. No imputation for missing values will be conducted. The minimum possible score is -3.06. The maximum is not defined.

Descriptive tables and plots as well results from the MMRM model will be provided as described in Section 4.5.1 and [Table 2](#) for cUHDRS, its individual components total raw scores, the 'maximal chorea in upper limb' item (left and right; from TMS) and the 'maximal chorea score'.

#### **4.5.1.4 Independence Scale**

The patient's Independence Scale (IS) is the Investigator's assessment of the patient's degree of independence. The scale consists of 19 discrete levels ranging from 10 to 100 (by 5) where no special care needed corresponds to a scale of 100 and tube fed and total bed care corresponds to a scale of 10.

The scale is not considered completed if there is no result available. There will be no imputation for missing data.

Descriptive tables and plots (as continuous score) as well results from the MMRM model will be provided as described in Section 4.5.1 and [Table 2](#).

#### **4.5.1.5 MRI Volumes and Boundary Shift Integrals**

A 3D T1-weighted structural MRI scan will be used to quantitate whole brain, caudate and intraventricular volumes. The only absolute measures are the structural volumes (baseline), while boundary shift integral (BSI) are used to assess changes in volumes over time. Three boundary shift integrals will be considered: K-means ventricular boundary shift integral (VBSI), K-means caudate boundary shift integral (CBSI) and K-means brain boundary shift integral (KNBBSI). To be noticed is that BSI values represent already a measure of change from baseline.

The affine scaling factor will be used for normalizing volumetric imaging values (both absolute volumes and BSI), in order to remove the confounding influences of the head size of the patients. Normalized versions are derived as follow:

$$\text{VOLn} = \text{VOL} / \text{ASF}$$

$$\text{BSIn} = \text{BSI} / \text{ASF}$$

where ASF= Affine Scaling Factor and VOL= absolute structural volumes

Normalization is not required for BSI percent change from baseline (or annualized percent change) given that:

$$\text{BSI\_percent-change} = \text{BSI} / \text{VOL} * 100 = \text{BSIn} / \text{VOLn} * 100$$

Only data with a QC flag equals to 'Pass' will be used in the analyses.

Descriptive tables and plots as well results from the MMRM model will be provided as described in Section 4.5.1 and [Table 2](#).

#### **4.5.1.6 Clinical Global Impression-Severity and Clinical Global Impression-Change**

The CGI-S is a single-item measure of current global severity. The CGI-S is assessed using an 11-point numeric rating scale (NRS) where higher scores indicate greater severity (0="not at all severe" to 10="Extremely severe", by 1).

The CGI-C is a single-item measure of change in global status (from baseline). The CGI-C has seven response options: "very much worse," "much worse," "minimally worse," "no change," "minimally improved," "much improved," and "very much improved". To assess the relevance of this change, a follow-up question with dichotomous response options ("yes" or "no") asks if the change has had a meaningful impact on the patient's wellbeing.

There will be no imputation for missing data

Descriptive tables and plots for CGI-S (as continuous) and CGI-C (as categorical) will be provided as described in Section 4.5.1 and [Table 2](#).

For CGI-C descriptive statistics of the number and percentage of patients with each score will be summarized by visit.

For CGI-S change from baseline in will be summarized at each visit, where change from baseline is calculated as the post-baseline score minus the score assigned at the baseline assessment time point; in addition, negative values will be mapped to a category of "Improvement", zero values will be mapped to "No Change", and positive values will be mapped to "Worsening". The number and percentage of patients within each of these categories will be summarized by visit.

#### **4.5.1.7      Patient Global Impression-Severity and Patient Global Impression Change**

The PGI-S is a single-item measure of current global severity. The PGI-S is assessed using an 11-point NRS, where higher scores indicate greater severity (0="not at all severe" to 10="Extremely severe" by 1).

The PGI-C is a single-item measure of change in global status (from baseline). The PGI-C has seven response options: "very much worse," "much worse," "minimally worse," "no change," "minimally improved," "much improved," and "very much improved". To assess the relevance of this change, a follow-up question with dichotomous response options ("yes" or "no") asks if the change has had a meaningful impact on the patient's wellbeing.

Descriptive tables and plots for PGI-S (as continuous) and PGI-C (as categorical) will be provided as described in Section [4.5.1](#) and [Table 2](#).

For PGI-C descriptive statistics of the number and percentage of patients with each score will be summarized by visit.

For PGI-S change from baseline will be summarized at each visit, where change from baseline is calculated as the post-baseline score minus the score assigned at the baseline assessment time point; in addition, negative values will be mapped to a category of "Improvement", zero values will be mapped to "No Change", and positive values will be mapped to "Worsening". The number and percentage of patients within each of these categories will be summarized by visit.

#### **4.5.1.8      World Health Organization Disability Assessment Schedule (2.0)**

The WHODAS 2.0 (12-item version) assesses disability and aspects of health related quality of life (HRQoL). It is intended for use in any disease population, and it is linked to the concepts in the [International Classification of Functioning, Disability, and Health](#).

The 12-items version contains 12 items scored on a 0-4 Likert type scale, where higher scores indicate greater difficulty. The total raw score is the sum of the 12 scored items, which is then converted onto a 0–100% point scale (by dividing by 48 and multiplying by 100; [Manual for WHO Disability Assessment Schedule, WHODAS 2.0](#)).

There are 3 additional questions that are not part of the total raw score and are administered to assess overall difficult and activity impairment measured as number of days of inability over the past 30 days (values from 0 to 30).

The WHODAS 2.0 will be completed by both the patient and study companion (if available, about the patient) at baseline and post-baseline clinic visits on an electronic device.

Missing values will not be replaced and total score derived only if all items are present. The assessment is considered completed if none of the core 12 items are missing.

Descriptive tables and plots will be provided as described in Section 4.5.1 and Table 2 for the patients and study companion versions for the overall converted score (as continuous variable).

#### **4.5.1.9 Work Productivity and Activity Impairment**

The WPAI contains 6 items assessing the impact of disease on employment status (yes/no), hours missed due to disease, hours missed due to other reasons, hours worked, and impact on productivity and on daily activities (both using an 11-point NRS, from 0 to 10, where higher scores indicate greater impact). The following sub-scores will be computed (WPAI Scores):

- Percent work time missed due to problem:  $Q2/(Q2+Q4)$
- Percent impairment while working due to problem:  $Q5/10$
- Percent overall work impairment due to problem:  
 $Q2/(Q2+Q4)+[(1-(Q2/(Q2+Q4)))\times(Q5/10)]$
- Percent activity impairment due to problem:  $Q6/10$

The WPAI will be completed by the patient and study companion (if available, about him/herself). It will be completed monthly by the patient remotely on the Roche HD mobile app and by the study companion remotely on an electronic device.

Missing values will not be replaced and scores derived only if the items used to compute the score are present. The assessment is considered completed if there are no missing items. The assessment will be used for informing pharmaco-economic evaluations and will not be reported in the CSR.

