Speech difficulty is a common issue (with both cognitive and motor deficits impacting ability) and will be measured by a novel single-item measure, the Huntington's Disease–Speaking Difficulty Item (HD-SDI).

The clinician will complete a Clinical Global Impression of Severity (CGI-S) at baseline and a Clinical Global Impression of Change (CGI-C), and the patient will complete the Patient Global Impression of Severity (PGI-S) and the Patient Global Impression of Change (PGI-C).

Concepts such as health-related quality of life (HRQoL), health state utilities, and societal impacts (e.g., work productivity) are of particular interest to European Health Technology Assessment agencies. The WHO Disability Assessment Schedule 2.0 (WHODAS 2.0) and the EuroQol 5-Dimension, 5-Level (EQ-5D-5L) Questionnaire will assess HRQoL and health state utilities, respectively. The Work Productivity and Activity Impairment (WPAI) Scale will capture changes in employment status, including a reduction of work hours or loss of productivity.

Further details on these assessments are included in Section [4.5.10](#).

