## **4.2 ANALYSIS OF STUDY CONDUCT**

Population for analysis of study conduct will be all enrolled patients unless stated otherwise. All major protocol deviations will be listed and summarized. Number of patients enrolled will be summarized per center and country level. Reasons for discontinuation from study will be listed and summarized.

Time on study (in days) will be calculated as end of study visit (or withdrawal) date – reference date+1 (for definition of reference date see Section 4). Summary tables for time on study will be presented.

For each of the outcome assessments (patient-, observer- and clinician-reported, and performance) the number and proportion of patients (or observer where applicable) who completed the assessment (among those expected to complete the assessment) will be summarized at each time point. For this analysis the ITT population will be used but for safety assessments (e.i. C-SSRS), where the safety population will be used instead. For the evaluation of completeness of each outcome assessment please refer to each subsections within Section 4.5.1 and Section 4.7.7.

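### The WPAI scoring and completion rules in SAP 4.5.1.9 do not separate items that do not apply from missing items, so a score already fixed at 100% can be withheld and non-employed respondents count as not completed

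*SAP*

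**What the plan says.** SAP Section 4.5.1.9 lists six WPAI items, in this order: "employment status (yes/no), hours missed due to disease, hours missed due to other reasons, hours worked, and impact on productivity and on daily activities". From them it defines four scores: work time missed, impairment while working, overall work impairment and activity impairment. Two rules then apply. On scoring: "Missing values will not be replaced and scores derived only if the items used to compute the score are present". On completion: "The assessment is considered completed if there are no missing items". Neither rule has an exception for a respondent who worked no hours or who has no job.

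The completion rule feeds SAP Section 4.2, where for each outcome assessment the number and proportion "who completed the assessment (among those expected to complete the assessment) will be summarized at each time point". SAP Section 4.8 adds no missing-data rule for outcome assessments; it refers back to Sections 4.5.1 and 4.7.7.

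Protocol Section 3.3.2.1 gives the purpose of the instrument: it "will capture changes in employment status, including a reduction of work hours or loss of productivity". The WPAI is completed monthly and remotely, with no clinic administration (SAP Section 4.5.1.9; Protocol Appendix 3). Its results go to pharmaco-economic work and stay out of the clinical study report.

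**The concern.** Some WPAI items have no meaningful answer for some respondents. A person who did no work in the period has no working time in which to rate productivity, and a person without a job has no hours to report. A rule that treats every blank alike handles these respondents as if they had failed to answer.

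Two things are at stake. First, a respondent whose week was lost entirely to the disease can drop out of the overall work impairment score even though the answers given already fix its value. Such a loss is informative, because it removes a worst-case outcome. Second, compliance looks poorer than it is, and increasingly so if respondents leave work during follow-up. In addition, stopping work, which the protocol says the instrument is there to capture, enters none of the four scores.

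**Working it through.** **Inputs.** All are from SAP Section 4.5.1.9. The item numbers are inferred from the order of the list and fit the formulas: Q1 employed, Q2 hours missed because of the disease, Q3 hours missed for other reasons, Q4 hours worked, Q5 effect on productivity (0 to 10), Q6 effect on daily activities (0 to 10). The SAP states no figure on this point, so there is none to reproduce.

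**Formulas.**
- Work time missed: A = Q2/(Q2+Q4)
- Impairment while working: Q5/10
- Overall work impairment: A + (1−A) × Q5/10
- Activity impairment: Q6/10

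**An ordinary record.** Q2=8, Q4=32, Q5=3: A = 8/40 = 0.20, and overall = 0.20 + 0.80 × 0.30 = 0.44, or 44%.

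**No hours worked because of the disease.** With Q2>0 and Q4=0, A = Q2/Q2 = 1 and overall = 1 + 0 × Q5/10 = 1. Evaluating the formula for every Q2 from 1 to 60 and every Q5 from 0 to 10 gives exactly 100% each time, so Q5 carries no information here. With Q2=40, Q4=0 and Q5 blank, the SAP rules give:
- work time missed: 100%, derived;
- impairment while working: not derived;
- overall work impairment: not derived.

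By contrast, Q2=39, Q4=1, Q5=5 is scored: 39/40 + (1/40) × 0.5 = 0.975 + 0.0125 = 98.75%.

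**Not employed.** With Q2, Q4 and Q5 blank, none of the three work scores is derived; only Q6/10 remains. With the hours entered as zero, A = 0/0, so work time missed and overall impairment are still undefined; impairment while working exists only if Q5 was answered.

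**Completion.** A non-employed respondent who answers Q1 and Q6 and leaves the work items blank has missing items, and so is not completed under the rule.

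**Effect on a mean overall score.** Let f be the share of employed respondents who missed the whole week and left Q5 blank, and m the mean overall score in the rest. The mean with them included is f + (1−f)m; with them dropped it is m. The understatement is f(1−m). The documents give neither f nor m. The values below are assumptions, and the results are in percentage points:

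| m | f = 2% | f = 5% | f = 10% |
|---|---|---|---|
| 20% | 1.6 | 4.0 | 8.0 |
| 30% | 1.4 | 3.5 | 7.0 |
| 40% | 1.2 | 3.0 | 6.0 |

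**The case against.** The strongest reply is that the first part depends on a form that neither document reproduces. If the device forces an answer to Q5, the overall score comes out at 100% and nothing is lost. The SAP also cites an outside scoring source, which cannot be consulted here. This stands: the loss is conditional on a blank Q5.

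Three stronger readings are tempting, and the documents do not support them.
- A reader might infer that the rule always removes the top of the scale. It does not. Q2=40, Q4=5, Q5=10 gives 40/45 + (5/45) × 1 = 100%, and that score is kept.
- A reader might infer that each step of decline takes the patient out of the WPAI. It does not. An employed respondent off work all week keeps work time missed at 100%, and activity impairment needs only Q6. Loss of the work scores after leaving employment follows from their definition (0/0) as much as from the missing-data rule.
- A reader might infer that a reported mean is too low by a definite number of points. The SAP plans no such mean: the WPAI is absent from Table 2, and the pharmaco-economic analysis is not described.

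It can also be said that work is assessed elsewhere, through the occupation item of the Total Functional Capacity scale (SAP Section 4.5.1.3.1). That is true, so loss of work capacity is not invisible in the study. But that item is one investigator-rated part of a total score and does not supply the WPAI output that the protocol's stated purpose suggests.

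Two further objections do not stand. One is that a 100% rule ignores Q3, so that Q2=1, Q3=39, Q4=0 would score 100%. The SAP formula already gives 100% for that record when Q5 is answered, so the rule only makes the blank-Q5 case consistent with it. The other is that SAP Section 4.2 counts only those expected to complete the assessment. A non-employed respondent is still expected to answer Q1 and Q6, and the SAP does not say otherwise.

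**Conclusion.** The point holds in a limited form. As written, the scoring rule withholds an overall work impairment score that Q2 and Q4 alone fix at 100%, provided Q5 is blank when Q4=0. The completion rule counts a non-employed respondent as not completed if the work items that do not apply are left blank. No planned score uses Q1, although the protocol gives changes in employment status as a purpose of the instrument. No other section of the SAP repairs this.

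The size cannot be given from the documents. The direction for the mean overall score is downward, by f(1−m); the 1.2 to 8.0 points in the table are illustrations on assumed inputs. No primary or secondary endpoint is touched. The consequence is confined to the pharmaco-economic use of the WPAI and to the completeness summary, so this is a minor correction.

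**What to change.** Amend SAP Section 4.5.1.9 as follows.
1. Set overall work impairment to 100% when Q2>0 and Q4=0, whether or not Q5 is present. This evaluates the existing formula and imputes nothing. A record with Q2=Q4=0 stays underived.
2. Define a completed assessment as one with all applicable items answered; for a non-employed respondent these are Q1 and Q6.
3. State that the work scores apply to employed respondents, and show the number and proportion employed (Q1) at each monthly assessment beside them. Count stopping work from the first available WPAI, since no baseline clinic administration is scheduled.

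The cost is a few sentences and one small summary from data already collected. As the SAP has no WPAI table, the employment figures would go wherever the work scores are presented. If the device turns out to force an answer to Q5, the first change alters nothing and does no harm.
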